Participants will be compensated up to \$125 for their participation in Aim 1; \$125 will be evenly divided among the total number of interviews needed to compensate participants for their involvement with each interview.

Aim 2

All participants will be initially screened via EMR records for potential eligibility (type of HNC, date(s) of treatment, age, sex, race, and education, etc.). A waiver of authorization for this access has been requested below. Study staff will seek permission to approach potential participants from the HNC survivor's provider before inviting the patient to extend an existing scheduled appointment to participate in the study. At the end of the clinic visit, the HNC survivor will meet with the study staff to obtain informed consent, schedule another time to discuss the study or obtain contact information to send the consent document (i.e., via REDCap or mail). After consent, the coordinator will record baseline data and all assessments. Participants that are found to have clinically significant depression (≥ 16 on the CES-D Iowa short form) will be withdrawn from the study and referred to social work.

Consented participants will then be block-randomized into one of 2 arms:

- i. **Control condition: Assessment and Feedback (AF).** Regardless of drinking level ascertained during the baseline questionnaires, the patient will receive feedback about their reported alcohol consumption from study coordinators (i.e. not through Bottle Cap). Feedback will be provided by study coordinators one time, in person or virtually (depending on how the participant elects to receive their baseline visit), after the baseline measures are completed, and include assessment of alcohol levels and recommending alcohol cessation. The feedback will emphasize that, according to leading medical associations, any consumption of alcohol is not advisable for cancer survivors, as continued

alcohol use is associated with a higher risk of cancer recurrence and reduced quality of life. A sample feedback statement is “one or two drinks might not seem much, but it can increase your chances of cancer recurrence”. Smoking cessation information will also be provided as per usual care. Patients will be urged to stop smoking and referred to a smoking cessation program if so desired. Participants will be asked to complete two follow-up questionnaires, one at 3 and one at 6 months post baseline, during scheduled follow-up visits. No further effort will be required.

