17. RISKS TO SUBJECTS

- *Describe any potential risks and discomforts to the subject (physical, psychological, social, legal, or other) and assess their likelihood and seriousness and whether side effects are reversible. Where appropriate, describe alternative treatments and procedures that might be advantageous to the subjects.*
- *Include risks to others, like sexual partners (if appropriate)*
- *Discuss why the risks to subjects are reasonable in relation to the anticipated benefits and in relation to the importance of the knowledge that may reasonably be expected to results*
- *Describe the procedures for protecting against or minimizing any potential risks, including risks to confidentiality, and assess their likely effectiveness.*

[There is a slight risk that participants might be distressed or uncomfortable when being asked questions about their cancer or drinking habits. All research personnel with patient contact will be trained by [name] and the Co-Is to be vigilant and sensitive to expressions of distress. All participants will be encouraged to contact the PI if any concerns arise.

The risks to subjects are reasonable in that this is a minimally invasive study, no subject's treatment will be altered in any way and the only potential risk is that of distress with questions being asked which they are free to skip. The risks are outweighed by the anticipated benefits and knowledge to be gained that may help HNC survivors in addition to providing subjects with enhanced knowledge and awareness of the risks of alcohol consumption after cancer treatment.

The procedures to protect subjects against or minimize the described risks in addition to risks to confidentiality include allowing participants to skip or choose not to respond to any questions that may cause them distress. Confidentiality will be protected by ensuring that all patient information gathered will be kept on Northwell's secured server and in password protected files that only the research team has access to. Further, information will only be accessed when needed and the research team will be trained to ensure confidentiality and the correct procedures when accessing and saving patient information are used.

In the future, we may publish results of this study on data sharing websites (e.g., Open Science Framework), in scientific journals, and may present it at scientific meetings. If we do we will not identify the subject. All data included in the publication will be de-identified.

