18. RESEARCH RELATED HARM/INJURY

- *Describe the availability of medical or psychological resources that subjects might need as a result of anticipated problems that may be known to be associated with the research.*
- *If the research is greater than minimal risk, explain any medical treatments that are available if research-related injury occurs, who will provide it, what will be provided, and who will pay for it.*

[This study presents no greater than minimal risk to participants, thus research related harm/injury is not expected.]

Patients may be at risk for slight emotional distress, which might result from being asked questions about personal cancer and treatment experiences. Participants will be informed during the interview sessions and at the beginning of the assessment that potentially sensitive topics will be discussed and that they may skip any part that would make them uncomfortable. In accordance with Monter's standard of care procedures, any participant who expresses distress throughout the duration of this study, for any reason, will be referred by the study team to a licensed social worker from our institution. Patients will also be referred to social work if they are clinically depressed or found to have severe substance abuse, as evaluated by our baseline assessment of standardized measures]

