21. COSTS TO SUBJECTS

- *Describe any foreseeable costs that subjects may incur through participation in the research*
- *Indicate whether research procedures will be billed to insurance or paid for by the research study.*

[This study uses text messaging to deliver notifications, reminders, and study questionnaires. Completing the surveys will require cellular data if a participant is not connected to Wi-Fi. Standard message and data rates from the participant’s wireless carrier may apply. Study participants will not be compensated for any costs related to data usage or sending or receiving text messages by the study or by members of the study team.

If referred for counseling or medical care, the study will not be responsible for any costs associated for future counseling or medical care needed by participants.]

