In the event a participant experiences difficulty navigating our electronic consent form, the study team will mail a written copy of the consent form to the participant. If the participant agrees to participate, they will be directed to sign the consent form and return back to the study team. This can be accomplished electronically (i.e., scanned copy of consent form sent to the study team) or via mail (i.e., study team provides stamped return envelope for participants to mail back consent form).

Research coordinators will review names and signatures of all completed consent forms. PDF copies of signed consent forms will be stored in a HIPAA-secured, Northwell approved storage drive with protected access to only the PI and research personnel listed on the study protocol. A copy of the signed form will be made available to participants.

Participants may contact a member of the research team with questions about the research. Each page of consent materials will contain a direct number to a research phone and a designated encrypted email inbox. Both the research phone and email inbox will be monitored daily by consenting coordinators.

In the state of NY, any participants under the age of 18 are considered children. If your study involves children, additional information should be provided to describe:

- *How parental permission will be obtained*
- *From how many parents will parental permission be obtained*
- *Whether permission will be obtained from individuals other than parents, and if so, who will be allowed to provide permission. The process used to determine these individual's authority to consent for the child should be provided*
- *Whether or not assent will be obtained from the child*
- *How will assent be documented*
- *Whether child subjects may be expected to attain legal age to consent to the procedures for research prior to the completion of their participation in the research. If so, describe the process that will be used to obtain their legal consent to continue participation in the study. Indicate what will occur if consent is not obtained from the now-adult subjects.*

| |
|----|
| NA |
|----|

If the study involves cognitively impaired adults, additional information should be provided to describe:

- *The process to determine whether an individual is capable of consent*
- *Indicate who will make this assessment*

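### Northwell coordinators advise every randomised participant to stop drinking, but the plan has no medical step triggered by the baseline alcohol score and does not list alcohol withdrawal as a risk

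*Combined protocol and SAP*

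**What the plan says.** Section 7 (Eligibility Criteria) requires confirmed drinking. It sets no upper limit and does not exclude people with alcohol dependence or past withdrawal.

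Section 11 (Research Procedures, Aim 2, control condition) says: "Regardless of drinking level ascertained during the baseline questionnaires, the patient will receive feedback about their reported alcohol consumption from study coordinators". The feedback is given once, in person or virtually, "after the baseline measures are completed, and include assessment of alcohol levels and recommending alcohol cessation". The intervention condition receives everything the control condition receives, plus cessation texts for 3 months. The advice therefore reaches every randomised participant. Those scoring 16 or more on the CES-D short form are withdrawn before randomisation.

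Section 18 (Research Related Harm/Injury) refers patients to social work if they are clinically depressed or "found to have severe substance abuse, as evaluated by our baseline assessment of standardized measures". It names no instrument, score or quantity for the alcohol part.

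Section 17 (Risks to Subjects) states that "the only potential risk is that of distress with questions being asked which they are free to skip", and otherwise deals with confidentiality. Section 15 expects no adverse events, because procedures are limited to texts and questionnaires.

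**The concern.** The trial is built to make people stop drinking: cessation is the primary clinical endpoint in Section 10. In someone physically dependent on alcohol, stopping can itself cause harm. That is general clinical knowledge rather than a statement in the documents, and it is the one outside premise used here.

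The plan collects the AUDIT and TLFB at baseline, so heavy use is visible to the study before the advice is given. As written, a coordinator can see a very high score, recommend cessation and refer to social work on personal judgement of what counts as severe. The plan requires no clinician to learn of the score. The next scheduled assessment is at 3 months (Section 9). What is at stake is participant safety; the estimates and tests are not affected.

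**Working it through.** The plan states no figure on this point, so the check sets the relevant texts side by side.

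**1. Who receives the advice.** Section 7 has no upper limit. Section 11 gives the feedback at every drinking level and repeats it in the intervention arm. Every randomised Northwell participant is therefore covered.

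**2. What the baseline alcohol score triggers.** Section 18 gives one action, social-work referral. The same sentence covers depression, and the two conditions compare as follows:

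- Depression: a CES-D cut-off of 16 and a stated action, withdrawal plus referral (Sections 7 and 11).
- Severe substance use: no cut-off, and referral to social work only (Section 18).

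**3. Whether the score is available in time.** Yes. Section 6 has AUDIT and TLFB collected at the baseline visit, and Section 11 places feedback after the baseline measures. The AUDIT branching in Section 12 skips the remaining items only for those who answer that they never drink, so enrolled drinkers are presented with the full scale.

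**4. Whether another provision supplies a medical step.**

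- Section 6: provider permission to approach comes before the baseline score and defaults to assent after one week without a reply.
- Section 15: adverse events are reported to the IRB, and serious ones go on their own form. This acts after the event.
- Section 16: the investigators or the IRB may withdraw a participant when continuing would not serve that person. This is discretionary and not linked to alcohol.
- Section 17: "All participants will be encouraged to contact the PI if any concerns arise".
- Section 18: "any participant who expresses distress throughout the duration of this study, for any reason, will be referred by the study team"; the referral is to a licensed social worker.
- Section 21: "If referred for counseling or medical care, the study will not be responsible for any costs associated". This is a cost clause with no trigger or pathway.
- Section 23: "Both the research phone and email inbox will be monitored daily by consenting coordinators".
- Section 27: monthly review of data and safety concerns, which anyone may also raise between meetings.

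The contact routes and distress referral depend on the participant recognising and voicing a problem. None of the provisions is a medical step triggered by the score.

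**5. Whether alcohol withdrawal is mentioned.** In the text available, withdrawal means leaving the study. Alcohol withdrawal, tapering and detoxification do not appear.

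**6. Number covered.** Section 8 plans 34 + 35 = 69 at Northwell. With 69 from the VA, the total is 69 + 69 = 138. Northwell reaches 138 only if it makes up the entire VA shortfall. These are the numbers who receive the advice, not the numbers at risk.

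**The case against.** The strongest reply is that the trial adds little risk. It gives brief, one-time advice that cancer organisations already give (Section 3), plus texts in one arm, to patients in regular oncology follow-up. No text tells anyone to stop abruptly. Section 3 also notes that patients often abstain during treatment, which may reduce dependence at enrolment, although eligibility at 3 months or more after treatment leaves later survivors in. All of this stands, and it is why the point calls for a small addition and does not oppose the advice.

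A reader might infer more than the documents support:

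- *That nothing responds to the baseline alcohol measures.* Section 18's referral does. What it lacks is a threshold and a medical component.
- *That participants get no withdrawal warning.* This cannot be known. The consent pages and message set were not available, and Section 11 gives only one sample feedback sentence. A warning could sit in any of them.
- *That harm would go unreported.* Section 15 provides adverse event reporting, and Section 27 provides monthly review.
- *That the number at risk can be read from Section 3.* Its 21.4% is a screening figure for problem drinkers among those still drinking at 12 months. It does not measure dependence or withdrawal risk.
- *That the VA site has the same gap.* Section 4 says the VA IRB reviews conduct there, so the point is confined to Northwell.

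**Conclusion.** The point holds as a participant-safety gap at Northwell. Cessation is advised at every drinking level, and the one score-linked step has neither a threshold nor a medical component. Section 17's statement that distress is the only potential risk is wrong for a trial that aims at cessation.

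The advice covers 69 planned participants, and at most 138. The share with severe use and the rate of withdrawal are not given, so no count of people at risk is offered. The recommendation does not need one, because Section 18 already anticipates such participants. The conclusion rests on the text available and on the premise that stopping can harm a dependent drinker. It is a change worth making, not a reason to stop the trial, and it implies no bias in the cessation comparison.

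**What to change.** 1. In Section 18, state one AUDIT/TLFB threshold chosen by the clinical investigators, and score it before feedback is given.
2. Above the threshold, keep the social-work referral and notify the treating clinician in parallel.
3. Give these participants the cessation feedback with a standard caution: do not stop abruptly without medical guidance, these are the warning signs of withdrawal, and this is the study contact number (Section 23).
4. Add alcohol withdrawal to the risks in Section 17 and to the monthly review in Section 27.
5. Do not hold feedback or texts until the clinician replies. Section 6 already anticipates providers who do not respond, and an open-ended hold could remove the assigned treatment from the heaviest drinkers for much of the 3-month text period. Stop feedback or texts only if the clinician objects. In that case keep the 3- and 6-month assessments and analyse in the assigned arm.

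The cost is small: a score flag on data already collected, one message per flagged participant, a short script addition and wording edits. TLFB quantities must be derived, and mailed or telephone responses scored, before the feedback contact. The downside is a slightly different script for a few heavy drinkers in both arms. Consent, randomisation and the 70% recruitment measure are unaffected.

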12. STATISTICAL ANALYSIS

- *Describe how your data will be used to test the hypotheses.*
- *State clearly what variables will be tested and what statistical tests will be used.*
- *Include sample size calculations.*
- *If this is a pilot study, state which variables will be examined for hypothesis generation in later studies.*

Aim 1:

All newly adapted Bottle Cap messages will be reviewed by the Patient Advisory Board (PAB), which consists of at least 15 HNC survivors from Northwell Health and 15 HNC survivors from the VA, as well as 5 clinicians (oncologists, surgeons, nurses, etc.) who care for HNC patients and survivors. Members of the PAB will be asked to rate, on a yes/no binary scale, whether a message is motivating and convincing. If 80% of members

rate a message on a binary scale as both motivating and convincing it will be included in the message bank. Further, during the individual interviews with members of the PAB, we will collect qualitative feedback on how best to adapt the messages so they are tailored to HNC survivors' unique issues related to alcohol use, as well as use language that resonates with civilians or VA members. Feedback supported by ≥ 2 HNC survivors will be integrated into the text messages.

Aim 2:

Power Analysis:

The proposed recruitment sample size of 69 participants per arm (138 participants total) is based on feasibility and availability of resources during the recruitment time frame, as estimated by the PI of this study. Assuming 15% attrition, recruitment of 69 participants per arm will yield an analytic sample size of approximately 60 participants per arm (120 participants total). One of the main goals of this study is to estimate the cessation rate in both the control arm and intervention arms. Therefore, in Table 1 we used two sample sizes to calculate the 95% exact confidence intervals (CI) and widths/precision corresponding to four cessation rates. The limits are dependent on the observed proportion, but a sample size of 60 per arm will produce a two-sided 95% confidence interval with a maximum width equal to 25% when the sample proportion is as high as 40%.

Variables to be used in the main analyses (including covariates): We will collect data on demographics, health history and treatment type, physician cessation advice, overall health, and alcohol use. Additionally, we will collect data on acceptability of the text-message based intervention and feasibility of conducting a future RCT of the intervention. Our primary analyses will involve a binary measure of alcohol cessation using the TLFB and AUDIT scales. In order to facilitate a binary measure, the AUDIT questionnaire will be modified to include branching logic to not present the remaining questions of the questionnaire to participants should their response to the first question of “How often do you have a drink containing alcohol?” be “never”. the TLFB will be supersede the AUDIT as the primary outcome measure if conflicting responses are provided. Secondary exploratory analyses will involve measures of quality of life, depression, social isolation, and loneliness as well as percent change of alcohol cessation.

Statistical Analyses:

Summary scales of standardized measures will be computed. Univariate and descriptive analyses will be performed on all continuous outcome variables and, normalizing and/or variance stabilizing transformations will be conducted. We will examine the data for outliers and use descriptive and inferential statistical techniques for data characterization. We will compare differences between the AF and intervention arms with a 2x2 chisquare test on the proportions of cessation in the groups. In addition, the rate of cessation between civilian and Veteran patients will be preliminarily evaluated through a t-test or analysis of variance procedure.

Stratification of data:

Patients, who have consented to participate, will be randomized to either the intervention or to the comparison condition (assessment and feedback about alcohol use). This procedure will ensure that an even number of participants will be allocated to the two arms, and that even numbers per condition across sites (i.e., Northwell and VA) are maintained overall. The Quantitative Intelligence team will develop and implement the randomization procedure, using a secure, HIPAA-compliant, web-based application that allows investigators or the research coordinator to randomize subjects into RCTs, using their personal computer and allows for multicenter, stratified, and single/double blinded RCTs, using permuted blocks.]

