during treatment, into early survivorship, and through long-term survivorship. A literature review on the prevalence and effects of alcohol consumption after oral cancer diagnosis indicates that between 34% and 57% of survivors of cancer of the upper aerodigestive tract (HNC and esophageal cancers) continue to drink after diagnosis. In a study retrospectively assessing alcohol use *before* HNC diagnosis, compared to immediately following diagnosis, the prevalence of alcohol use decreased by 16.7%, and the proportion of problem drinkers decreased from 46.6% to 24.5%. Although this is a considerable decrease, a quarter of the sample with newly diagnosed HNC continues to abuse alcohol. Other longitudinal research suggests that 44.5% of individuals with HNC were still drinking 12 months after diagnosis, with 21.4% of these individuals categorized as problem drinkers (defined as those who scored 3 or more on the Michigan Alcoholism Screening Test). During early and long-term survivorship, a substantial proportion of HNC survivors continue to consume alcohol. In a population-based study of HNC survivors longer than 6 months post-treatment, there was a mere 13% drinking cessation rate; 62% of the sample considered themselves current drinkers. Of those current drinkers, about a quarter of the sample (i.e., 26%) reported that they consume alcohol at least 4 times per week. A study of HNC survivors 5 years post-treatment reported that 38.9% continued to use alcohol. Studies suggest that HNC survivors are often unaware of the relationship between alcohol and HNC, and do not receive adequate information from their providers about the impact of alcohol on their disease course. In one study, between 15-50% of those surveyed did not recall having received any recommendation regarding alcohol consumption. Thus, education about, and raising awareness of, the risks of alcohol consumption among HNC survivors is a necessary first step to achieve alcohol reduction and cessation. **Therefore, there is an urgent need for alcohol cessation interventions for this growing group of HNC survivors, to prevent second malignancies and cancer recurrences, as well as to improve their psychosocial functioning. This need is escalated for military and veteran populations, who are prone to risky drinking behavior and for whom mission readiness depends upon their physical and mental health. Our proposal seeks to adapt and preliminarily evaluate an existing evidence-based alcohol cessation intervention, delivered via an existing text-message based platform called Bottle Cap, for HNC survivors in both civilian and VA settings.**

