Eligibility and permission to approach will be confirmed by the collaborating providers; if the provider does not respond to the request within one week, they will be assented by default. Study staff will contact survivors by phone and via myNorthwell to assess interest in the study. Once eligibility has been established, interested patients will be asked to meet study RCs after the regularly scheduled appointment, and to expect that the visit will be extended by 45-60 minutes. At the end of the clinic visit, the HNC survivor will meet with the RC to give informed consent, record baseline data, and assess drinking patterns with the AUDIT questionnaire and the Time-Line Follow Back (TLFB) alcohol use assessment procedure. Patients will also have the option to elect to consent and complete questionnaires virtually. Randomization will occur after the patient is consented. The RC will access the randomization website and provide alcohol use feedback, plus, if randomized to the intervention arm, register the HNC survivor with the Bottle Cap platform.

Survivors who have consented to participate will be block randomized to either AF or the intervention text messaging arm. This procedure will ensure that even numbers per condition across sites are maintained overall.

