7. ELIGIBILITY CRITERIA

- *Describe the characteristics of the subject population, including their anticipated number, age, ranges, sex, ethnic background, and health status. Identify the criteria for inclusion or exclusion of any subpopulation.*
- *Explain the rationale for the involvement of special classes of subjects, such as fetuses, pregnant women, children, prisoners or other institutionalized individuals, or others who are likely to be vulnerable. You cannot include these populations in your research, unless you indicate such in the protocol*
- *Similarly, detail exclusionary criteria: age limits, special populations (minors, pregnant women, decisionally impaired), use of concomitant medications, subjects with other diseases, severity of illness, etc.*

Healthcare Workers (Aim 1)

Inclusion Criteria:

- 1) Employed as a physician or nurse
- 2) Currently treating head and neck cancer patients (surgically or with radiation)

Exclusion Criteria:

N/A

Patient Advisory Board (Aim 1) and Participants (Aim 2)

Inclusion Criteria:

- 1) Adult male or female patients 18 years or older
- 2) Diagnosed with primary cancer of: pharynx (nasopharynx, oropharynx, hypopharynx), larynx (all subsites), oral cavity (all subsites)
- 3) Having completed surgical, radiation, and/or chemotherapy treatment;
- 4) Post-treatment completion status of at least 3 months;
- 5) Able to communicate and read in English;
- 6) Possess a telephone with text messaging capability; and
- 7) Confirmation of alcohol consumption.

Exclusion Criteria:

- 1) Non-English speaker
- 2) Non-drinker
- 3) Previously enrolled in Aim 1 **(for Aim 2 only)**]
- 4) Clinically significant depression, as indicated by an assessment of ≥ 16 on the CES-D 11-item Iowa short form scale **(Aim 2 only)**

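### The arm comparison of cessation makes no use of baseline drinking, which is measured before randomization; a prespecified adjusted risk difference would be a modest, nearly free gain in precision

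*Combined protocol and SAP*

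**What the plan says.** All references are to the combined protocol and SAP.

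- **Allocation.** Section 12 (Stratification of data) says that "even numbers per condition across sites (i.e., Northwell and VA) are maintained overall". Section 6 says the same. Site is the only balancing factor named. The web tool "allows for multicenter, stratified, and single/double blinded RCTs, using permuted blocks", but no other stratum is listed.
- **Entry.** The drinking criterion in Section 7 is only "Confirmation of alcohol consumption", with no minimum level.
- **Timing.** At the baseline visit, staff "assess drinking patterns with the AUDIT questionnaire and the Time-Line Follow Back (TLFB) alcohol use assessment procedure" (Section 6). Section 11 gives the order: "After consent, the coordinator will record baseline data and all assessments", and later "Consented participants will then be block-randomized into one of 2 arms".
- **Analysis.** The only method described for comparing the arms on cessation is a "2x2 chisquare test on the proportions of cessation in the groups" (Section 12, Statistical Analyses). Section 12 limits the study to descriptive and univariate analyses. Alcohol use is among the data listed under a heading that mentions covariates, but no model takes it up.
- **Purpose.** Section 12 (Power Analysis) makes the arm comparison a secondary, exploratory and unpowered objective. Its result is meant to serve as an effect size for future trials.

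**The concern.** The sample will mix occasional drinkers with people who drink on most days. Section 3 reports, for current drinkers in an earlier cohort of survivors, that "about a quarter of the sample (i.e., 26%) reported that they consume alcohol at least 4 times per week". If people who drink less find it easier to stop, baseline drinking is prognostic for the primary outcome. With about 59 analysed per arm, chance alone can give one arm clearly more of the heavier drinkers. Neither the allocation nor the analysis would correct for that, so part of the observed difference would reflect who was in each arm. At stake is the accuracy of the effect size passed on to a larger trial.

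**Working it through.** **The plan's own figures.** For 20% against 30%, two-sided 0.05, 80% power, pooled variance:

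n = [1.96·√(2·0.25·0.75) + 0.8416·√(0.16 + 0.21)]² / 0.10² = 293.2, rounded up to 294 per arm. 294 / 0.85 = 345.9, or 346 recruited per arm. Both match Section 12.

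**Analysed number.** 69 × 0.85 = 58.65, or 59 per arm (Section 12 rounds to about 60).

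**Precision of the planned comparison.** SE = √(0.16/59 + 0.21/59) = 7.9 points, so a 95% interval is about ±15.5 points.

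**How often the arms differ by chance.** Let p be the share of heavier drinkers. I take p = 26% (the Section 3 figure, from another cohort) and p = 50% (an assumption). SD of the arm difference in that share = √(2p(1−p)/59), which is 8.1 points for 26% and 9.2 points for 50%.

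| Chance of a difference of 10 points or more, 59 per arm | p = 26% | p = 50% |
|---|---|---|
| Fixed pool of 118 split in two (hypergeometric) | 21% | 27% |
| Normal approximation | 22% | 28% |
| Independent binomial arms | 25% | 31% |

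The range is about 21% to 31%. The result is sensitive to whole-number counts. At exactly 60 per arm, a gap of 6 people is exactly 10 points, and the hypergeometric figures become 29% (p = 25%) and 36% (p = 50%).

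**What an imbalance does.** Shift = imbalance × (cessation in lighter minus cessation in heavier drinkers). The documents give no such gap, so I vary it: control cessation of 25/15%, 30/10% and 35/5%, each averaging 20% when p = 50%. A 10-point imbalance then shifts the difference by 0.10 × 10, 20 or 30 = 1, 2 or 3 points.

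**What adjustment gains.** Simulation of 40,000 trials, 60 per arm, p = 50%, uniform true effect of 10 points. The adjusted estimate is standardised over the two drinking levels. The last two columns are average errors in trials where the intervention arm has at least 15 points more heavier drinkers (about 5% of trials).

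| Gap | SD unadjusted | SD adjusted | Variance cut | Error, unadjusted | Error, adjusted |
|---|---|---|---|---|---|
| 10 | 7.9 | 7.9 | 0.5% | −2.0 | −0.2 |
| 20 | 7.8 | 7.6 | 4% | −4.0 | −0.2 |
| 30 | 7.9 | 7.4 | 12% | −5.9 | −0.2 |

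The mean unadjusted estimate over all trials was 10.0 points, so there is no bias on average. In participants, the gain runs from 1/0.9946 = 1.005 to 1/0.8832 = 1.13, or about 0.5% to 13% more. A repeat with 59 per arm gave variance cuts of 0.4%, 4% and 11% for p = 50%, and 0.2%, 3% and 7% for p = 26%.

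**The case against.** The strongest reply is that nothing is invalid here. Randomization makes the unadjusted difference unbiased, and an ordinary interval around it already covers chance imbalance. A shift of 1 to 3 points is small against a 7.9-point standard error. The plan calls the comparison exploratory and unpowered, and it justifies the sample size by per-arm intervals, which adjustment of the difference does not sharpen. No passage says how well baseline drinking predicts cessation; with a 10-point gap the gain is close to nothing. All of this stands, and it sets the size of the point.

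Another reply is that alcohol use already appears under a heading that mentions covariates. That shows the intention may exist. But no adjusted analysis follows, and the stated scope is univariate, so the role of the variable is left open.

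A reader might infer three stronger things, and the documents support none of them:

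- That the cessation difference is biased. The error is conditional on an unlucky draw and averages out to zero.
- That baseline drinking is known to be a strong predictor. This is plausible, but the documents do not quantify it.
- That balancing by site alone is a defect. Adjustment by itself removes nearly all of the conditional error. A cut at 4 or more times a week would be arbitrary: it measures frequency rather than quantity, and it comes from survivors more than 6 months after treatment.

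**Conclusion.** The point holds as a modest matter of precision. The plan collects a plausible prognostic variable before randomization and then leaves it out of the only comparison between arms. With 59 per arm, a difference of 10 points or more in the share of heavier drinkers occurs in about 21% to 31% of trials. Each 10 points moves the cessation difference by 1 to 3 points, against the 10-point difference used in the plan's illustration of a full trial. Adjustment cuts the variance by about 0.5% to 12%, and it removes an average error of about 2 to 6 points in the roughly 1 trial in 20 where the intervention arm is worst served.

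These sizes rest on assumptions: a heavier share of 26% to 50%, a lighter–heavier gap in cessation of 10 to 30 points, and the same 10-point effect at both drinking levels. If the gap is smaller than 10 points, there is almost nothing to gain. Exploratory status excuses low power. It is not a reason to forgo a correction that needs no more patients, in an estimate intended for future trials.

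**What to change.** In Section 12 (Statistical Analyses), keep the chi-square test and add one sentence: the cessation difference will also be reported as a risk difference adjusted for, or standardised over, baseline TLFB drinking level and site, with a 95% CI. State the form of the baseline variable (continuous, or a cut fixed in advance) before outcomes are seen by arm. A logistic model with arm, site and baseline drinking as main effects, averaged over the whole sample, avoids sparse cells if VA enrolment falls short. Name this as the use of alcohol use as a covariate, and amend the description of the study as univariate to match.

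The cost is a few lines of text and a little analyst time. No new measure, visit or participant is needed.

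Optionally, and only if randomization has not started, add baseline drinking as a second stratification factor beside site, with allocation opened once baseline TLFB and AUDIT are entered. That makes four strata instead of two and a few more incomplete blocks, and it adds little once the analysis is adjusted.
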